5.2. ELIGIBILITY

A subject is defined as eligible if all inclusion and exclusion criteria are fulfilled as it is described in the protocol. For details see CIP.

For tables to be created for the interim/annual and final reports, see chapter 6.2 and tables list 6.2.2.

5.3. WITHDRAWAL / FOLLOW-UP

If, during the clinical investigation, a subject must be prematurely withdrawn from clinical investigation, procedures are outlined in the CIP. These procedures should not interfere with the initiation of any new treatments that are necessary to treat a subject's condition. Information on all withdrawn subjects will be documented.

The following tables will be created for interim/annual and final reports related to the numbers of withdrawn subjects (if any):

Evaluation	Level of	Analysis Plan
Variable / Question	Measurement	
All Forms – Overview & Progres	s Report	
Counting of withdrawn subjects Number of Subjects Withdrawn by Site (Variable(s): SITENUM; COMPPROT; PRIMRSN)	Qualitative, nominal	Proportions, frequencies, column and row totals, missing proportion (if any).
Counting of withdrawn subjects Number of Subjects Withdrawn by Site by Visit (Variable(s): SITENUM; COMPPROT; PRIMRSN; VISITDT)	Qualitative, nominal	Proportions, frequencies, column and row totals, missing proportion (if any).
Comments related to Reasons for Subjects Withdrawn (Variable(s): RSNSPF)	Text, String	Listing of reasons for subjects being excluded by subject code/ID

Table 5.3: Withdrawal Tables List

5.4. ADHERENCE AND CIP DEVIATIONS

Any CIP deviations will be listed in the interim/annual and final reports. It is optional to describe this chapter in free text or present it in a tabulated format.

6. Analysis

The following tabulated analysis plan reflects this approach and specifies the variables characteristics (quantitative or qualitative) in detail together with the related analysis strategy. This also includes calculation and summaries based on primary elements and the required analysis.

In addition, it will be defined in the text or directly in the tables below, if the variable must be included in an interim/annual report (IR) and/or in the final report (FR).

6.1. HARMS AND SAFETY

Categorization and definitions of (Serious-, Unanticipated-) Adverse Device Effects, (Serious-) Incidents are given in the CIP.

Evaluation Variable / Question	Level of Measurement	Analysis Plan	Iı	nclusio	on
Adverse Events / Incidents	incusur ement		IR	FR	N/A
Device-Related Adverse Event / Incident (Variable(s): AEEVENT; AEOTHER)	Qualitative, nominal	Proportions, frequencies, column and row totals, missing proportion (if any). Listing of other Events/Incidents.	х	х	
Describe the AE/Incident (Variable(s): AEDESCRP)	Qualitative, nominal	Listing of other Events/Incidents Description.			Х
Unanticipated Adverse Device Event? (Variable(s): AEUADE)	Qualitative, nominal	Proportions, frequencies, column and row totals, missing proportion (if any).	Х	Х	
Severity (Variable(s): AESEVER)	Qualitative, nominal	Proportions, frequencies, column and row totals, missing proportion (if any).	Х	Х	
Describe Treatment: (Variable(s): ACTTREAT)	Qualitative, nominal	Listing of Treatment Description.			X
Action Taken (Variable(s): ACTNONE; ACTMEDS; ACTSURG; ACTLABOT; ACTSHORT; ACTPROHS; ACTOTHER: ACTOTHSP)	Qualitative, nominal	Proportions, frequencies, column and row totals, missing proportion (if any). Listing of given Other specifications.			X
AE Resolution (Variable(s): AERESOLV)	Qualitative, nominal	Proportions, frequencies, column and row totals, missing proportion (if any).			Х
Outcome (Variable(s): AEONWOTR; AEONWTTR; AEREWOTR; AEREWTTR; AETEDISB; AEPERMD; AESUEXP)	Qualitative, nominal	Proportions, frequencies, column and row totals, missing proportion (if any).			х
Creation of variable Number of Adverse Device Effects by Site (Variable(s): AEEVENT; SITENUM)	Qualitative, nominal	Proportions, frequencies, column and row totals, missing proportion (if any).	Х	Х	
Creation of variable Number of Adverse Device Effects per Subject and Site (Variable(s): AEEVENT; SITENUM; SUBID)	Qualitative, nominal	Proportions, frequencies, column and row totals, missing proportion (if any).	Х	Х	
Creation of variable Number of Adverse Device Effects by Visit (Variable(s): AEEVENT: VISNAME)	Qualitative, nominal	Proportions, frequencies, column and row totals, missing proportion (if any).		Х	

Table 6.1: Adverse Events / Incidents Tables List

Evaluation Variable / Question	Level of Measurement	Analysis Plan Inclusion		on	
Reoperation			IR	FR	N/A
Type of Procedure (Variable(s): TOPAMP; TOPDYNA; TOPIMPREM; TOPIRDEB; TOPRTAINTFIX; TOPINTSPF; TOPREVARTH; TOPARTHSPF; TOPRTAEXTFIX; TOPEXTSPF; TOPOTH; TOPOTHSPF)	Qualitative, nominal	Proportions, frequencies, column and row totals, missing proportion (if any). Listings of implant specifications.	Х	Х	
Reason(s) for Reoperation (Variable(s): DELUNION; IATRFRAC; IMPBRAK; IMPLFAIL; IMPLOOS; INFEC; MALILGN; MALUNI; NECRS; NONUNIO; PAIN; REOPOTH; REOPOTHSPF)	Qualitative, nominal	Proportions, frequencies, column and row totals, missing proportion (if any). Listings of other specifications.	х	х	

Table 6.2: Reoperation Tables List

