8.2. SECONDARY ENDPOINTS

- Safety: Incidence of device-related adverse events by 12 months will be monitored through collection and analyses.
- Efficacy/Performance: Bone consolidation will be assessed by 12 months as measured by Investigator assessment.

9. Selection of Clinical Investigation Population

Subjects participating in this clinical investigation will be recruited from the investigator's standard subject population, where all subjects presenting for treatment of tibial fractures will be evaluated for clinical investigation participation based on the eligibility criteria listed below.

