11.5.2. Final Analysis and Reports

The full final report with complete analysis and progress and conduct reporting will be created at the end of this clinical investigation.

12. Clinical Investigation Plan Deviations

A Clinical Investigation Plan (CIP) deviation is a departure from the approved CIP that is not implemented or intended as a systemic change. All CIP deviations are recorded and reported to each site's IRB/EC in accordance with the respective site's IRB/EC policies.

13. Adverse Events/Incidents

As this CIP is being carried out to satisfy the post-market requirements to support safety and efficacy/performance according to the Council Directive 93/42/EEC concerning medical devices (Annex X (1.1c)) (MDD 93/42/EEC) and Regulation 2017/745 on medical (MDR 2017/745), categorization and definition of device related adverse events will follow the guidelines outlined in the MDR 2017/745 as "incident" reporting. The following AE terminology will apply:

An Adverse Device Effect (ADE) is defined as any untoward or unintended response to the clinical investigation treatment; and/or a medical response which may have a causal relationship to the treatment.

- An Incident is defined as any malfunction or deterioration in the characteristics or performance of a device made available on the market, including use-error due to ergonomic features, as well as any inadequacy in the information supplied by the manufacturer and any undesirable side-effect.
- A Serious Adverse Device Effect (SADE) is defined as any ADE that results in consequences characteristic of a SAE or might lead to the consequences if suitable action or intervention is not taken; causes considerable interference with the subject's usual activities and may be incapacitating or life-threatening, including those events resulting in a subject's disability or permanent damage, or required intervention to prevent disability or permanent damage; results in a life-threatening illness or injury; and/or results in death (fatal).
- A Serious Incident is defined as any incident that directly or indirectly led, might have led or might lead to any of the following:
 - o the death of a patient, user or other person;
 - o the temporary or permanent serious deterioration of a patient's, user's or other person's state of health;
 - o a serious public health threat

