13.1. ADVERSE EVENT/INCIDENT SEVERITY

The severity of all AEs/incidents is assessed by the Investigator utilizing the following categories:

- **Mild:** The AE/incident is transient and easily tolerated by the subject.
- **Moderate:** The AE/incident causes the subject discomfort and interrupts the subject's usual activities.
- **Severe:** The AE/incident causes considerable interference with the subject's usual activities and may be incapacitating or life-threatening. This includes those events that result in a subject's disability or permanent damage, and/or required intervention to prevent permanent disability or damage.
- Life-threatening: The AE/incident results in a life-threatening illness or injury.
- **Fatal:** The AE/incident results in death.

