13.4. ADVERSE DEVICE EFFECT/INCIDENT REPORTING AND ANALYSIS

In the event that a SADE, UADE or serious incident occurs, the Investigator is required to notify the Sponsor within 48 hours of being made aware of the event. The Investigator is also required to notify their IRB/EC in accordance with the policies of their local laws and regulations.

14. Reoperations

Reoperations and reason(s) for reoperations will be collected throughout the course of the clinical investigation. A reoperation may include, but not limited to, irrigation and debridement, revision surgery, and/or implant removal.

15. Ethics

This clinical investigation is to be conducted according to International Conference of Harmonisation of Good Clinical Practice (ICH-GCP), applicable regulations, institutional research policies and procedures, Declaration of Helsinki and in compliance with the Clinical Investigation Plan (CIP). Investigators will be trained on the clinical investigation devices and surgical techniques prior to implanting clinical investigation subjects.

This CIP and any amendments will be submitted to a properly constituted independent ethics board, in agreement with local legal prescriptions, for formal approval of the clinical investigation conduct. The decision of the ethics board concerning the conduct of the clinical investigation will be made in writing to the Site Principal Investigator before commencement of this clinical investigation. Clinical investigations shall not begin until the governing regulatory authority has provided full, unconditional approval. Off-label use of the T2 Alpha Tibia Nailing System is not permitted.

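### SAP Table 6.1 has no row for serious device effects or serious incidents, and it keeps the action, resolution and outcome of device-related events out of every report

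*SAP*

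**What the plan says.** The protocol (CIP) states the secondary safety endpoint in section 8.2: "Safety: Incidence of device-related adverse events by 12 months will be monitored through collection and analyses". The synopsis says that safety will be demonstrated by reporting device-related intra-operative and post-operative events.

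CIP section 13 sets up a seriousness classification: "A Serious Adverse Device Effect (SADE) is defined as any ADE that results in consequences characteristic of a SAE". The definition goes on to cover effects that might lead to such consequences if nothing is done. A serious incident is defined in a similar way and includes incidents that might have led to death or serious deterioration. Section 13.4 attaches a duty to these classes: "In the event that a SADE, UADE or serious incident occurs, the Investigator is required to notify the Sponsor within 48 hours".

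On seriousness, SAP section 6.1 says only this: "Categorization and definitions of (Serious-, Unanticipated-) Adverse Device Effects, (Serious-) Incidents are given in the CIP". Table 6.1 then assigns each variable to report columns. The introduction to SAP section 6 explains that the text or tables define "if the variable must be included in an interim/annual report (IR) and/or in the final report (FR"; the third column is N/A. The row "Action Taken (Variable(s): ACTNONE; ACTMEDS; ACTSURG; ACTLABOT; ACTSHORT; ACTPROHS; ACTOTHER: ACTOTHSP" is ticked N/A only. So are the row "Outcome (Variable(s): AEONWOTR; AEONWTTR; AEREWOTR; AEREWTTR; AETEDISB; AEPERMD; AESUEXP" and the rows for resolution (AERESOLV), the event description and the treatment description. The rows for event type, unanticipated effect (AEUADE) and severity (AESEVER) are ticked for both reports.

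**The concern.** A trial that means to demonstrate safety by reporting device-related events should be able to say how many of those events were serious, how many were still open at the end and how many left lasting harm. The protocol makes sites identify serious events, and the SAP lists action, resolution and outcome as collected variables. None of this reaches a planned output. This is an explicit exclusion in the inclusion columns, not detail left for later, so an analyst who follows the SAP exactly will leave these results out of the final report.

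**Working it through.** No error rate, sample size or margin is involved, so the check is a row count and a comparison of definitions.

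**Row count of Table 6.1 (11 rows)**

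| Row | Interim/annual | Final | N/A only |
|---|---|---|---|
| Event type | yes | yes | |
| Event description | | | yes |
| Unanticipated effect | yes | yes | |
| Severity | yes | yes | |
| Treatment description | | | yes |
| Action taken | | | yes |
| Resolution | | | yes |
| Outcome | | | yes |
| Count by site | yes | yes | |
| Count per subject and site | yes | yes | |
| Count by visit | | yes | |
| **Total** | **5** | **6** | **5** |

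Taking out the three count rows leaves 11 − 3 = 8 descriptors. Of these, 5 are N/A only and 8 − 5 = 3 are reported. Rows for SADE or serious incident: 0.

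**Search for a seriousness variable.** CIP section 11 says that the SAP lists every variable. Across the whole SAP, seriousness appears only in the abbreviation list and in the section 6.1 sentence that points to the CIP for definitions. No listed variable flags a SADE or a serious incident.

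**Can the reported outputs stand in?**

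- *Unanticipated effects.* CIP section 13 limits these to events not described in the consent, the CIP or the labeling. CIP 13.3 itself lists 25 foreseeable events, including deep infection, compartment syndrome, pulmonary embolism, non-union and nail breakage. A serious case of any of them falls outside the AEUADE count.
- *Severity.* The Severe grade in CIP 13.1 begins "The AE/incident causes considerable interference with the subject's usual activities and may be incapacitating or life-threatening" and then adds disability, permanent damage and intervention to prevent them. One count therefore pools interference with activities and permanent damage. SADE and serious incident also include events with only potential serious consequences, which need not carry any particular grade. The Fatal grade does count device-related deaths, because CIP 13.2 captures device-related events only.
- *Reoperations.* Types and reasons are tabulated in both reports, but CIP section 14 does not restrict them to device-related events and the SAP does not link them to individual events.
- *Mortality.* The Kaplan-Meier analysis in SAP 6.7.4 takes any death as the event, without device attribution.
- *Withdrawals.* SAP 5.3 counts them by reason, which covers only events that ended participation.
- *Resolution.* No planned output says whether a device-related event resolved.

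**The case against.** The strongest reply is that the safety endpoint is incidence only, and that it is fully covered. The event-type rows give the counts, and SAP Table 6.6.3 adds a Kaplan-Meier analysis of time to the first device-related event. Seriousness, resolution and outcome are not in the endpoint wording. This stands. A reader might infer from Table 6.1 that the endpoint cannot be evaluated, and the documents do not support that.

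A reader might also infer that the reports will say nothing about serious or disabling events. That is too strong as well. Severe, Life-threatening and Fatal share much of their wording with the SADE definition, unanticipated effects by definition have actual or potential serious consequences, and reoperations, deaths and withdrawal reasons are all shown. Together they give a useful partial picture. They do not give a count of serious events, for the reasons set out in the working.

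Two limits also stand. The supplied protocol text gives no separate definition of SAE, so nothing here rests on a particular criterion such as hospital stay. The meanings of the outcome fields are inferred from variable names (AEPERMD and AETEDISB suggest permanent and temporary disability), because the case report form is not available.

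The overlap between Severe and Life-threatening in CIP 13.1 is a separate wording matter. It does not change a count of events graded Severe or worse and is not part of this point.

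**Conclusion.** The point holds in limited form. Table 6.1 has no SADE or serious-incident row and withholds 5 of 8 event descriptors from both reports. The planned outputs therefore cannot give three figures: the number of SADEs or serious incidents, the number of device-related events still unresolved, and the number with permanent harm short of death. The endpoint itself remains computable, and the tabulated outputs are a partial proxy for seriousness.

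The table ticks and the missing row can be read directly from the SAP. How many events would be affected cannot be estimated, because the documents give no expected number of device-related events or share that would be serious. That the existing outcome variable would supply the permanent-harm count is an assumption from its field names. The change should be made before the final report, but the point does not touch the primary analysis.

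**What to change.** In SAP Table 6.1:

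1. Move Action Taken, AE Resolution and Outcome from N/A to both the interim/annual and the final report. Their analysis cells already specify frequencies, so only the ticks change.
2. Add a SADE/serious-incident row with the number of events and the number of subjects, and a by-subject listing of each such event with its action, resolution and outcome. Populate it from the classification that sites must already make for the 48-hour notification. That notification covers SADEs, unanticipated effects and serious incidents together, so the class of each event must be recorded.

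The cost is a few more tables, plus either one yes/no eCRF field or a reconciliation of the event data with the notification records, because the SAP lists no seriousness variable. There is no added burden on subjects, and CIP 13.1 does not need to be amended for this.

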6.2. BASELINE CHARACTERISTICS

Evaluation Variable / Question	Level of Measurement	Analysis Plan	Inclusion		
Pre-Operative Visit Form – Sub Criteria	ject Eligibility –	Inclusion & Exclusion	IR	FR	N/A
Note: Inclusion and exclusion criteria wil fulfilled the inclusion criteria).	l be checked during r	nonitoring and reported by a state	ement (e	.g. all si	ubjects
Inclusion Criteria Questions (Variable(s): INCLA; INCLB; INCLC)	Qualitative, nominal	Proportions, frequencies, column and row totals, missing proportion (if any).			Х
Exclusion Criteria Questions (Variable(s): EXCLA; EXCLB)	Qualitative, nominal	Proportions, frequencies, column and row totals, missing proportion (if any).			Х

Table 6.2.1: Pre-Operative Visit Form - Subject Eligibility – Inclusion & Exclusion Criteria Tables List

Evaluation Level of Variable / Ouestion Measurement Analysis Plan		Inclusion			
Pre-Operative Visit Form - Sub	ject Demograph	ics	IR	FR	N/A
Creation of variable Age [years] Difference between Date of Surgery [dd.mm.yyyy] and Date of Birth/DOB [dd.mm.yyyy] in [years]] (Variable(s): BIRTHDT; VISITDT; VISNAME)	Quantitative, ratio	Case summary with number and percentage of valid cases/values, missing cases/values (if any) and total cases/values. Mean, median, interquartile range, maximum, minimum, standard deviation, 95% confidence interval for mean, Shapiro-Wilk Test.	х	х	
Gender (Variable(s): GENDER)	Qualitative, nominal	Proportions, frequencies, column and row totals, missing proportion (if any).	Х	Х	
Race (Variable(s): AMERIND; ASIAN; BLKAFR; NATHAW; CAUS; RACEOTH; RACEOTHR)	Qualitative, nominal	Proportions, frequencies, column and row totals, missing proportion (if any). Listing of given specifications.	Х	Х	
Height [captured in inches or cm] In the analysis, all values will be reported in inches and cm next to each other. (Variable(s): HGHTM)	Quantitative, ratio	Case summary with number and percentage of valid cases/values, missing cases/values (if any) and total cases/values. Mean, median, interquartile range, maximum, minimum, standard deviation, 95%			х

		confidence interval for mean, Shapiro-Wilk Test.			
Weight [captured in lbs or kg] In the analysis, all values will be reported in lbs and kg next to each other. (Variable(s): WEIGHTKG)	Quantitative, ratio	Case summary with number and percentage of valid cases/values, missing cases/values (if any) and total cases/values. Mean, median, interquartile range, maximum, minimum, standard deviation, 95% confidence interval for mean, Shapiro-Wilk Test.			х
Body Mass Index [kg/m²] (Variable(s): BMI)	Quantitative, ratio	Case summary with number and percentage of valid cases/values, missing cases/values (if any) and total cases/values. Mean, median, interquartile range, maximum, minimum, standard deviation, 95% confidence interval for mean, Shapiro-Wilk Test.	Х	х	

Table 6.2.2: Pre-Operative Visit Form - Subject Demographics Tables List

Evaluation Variable / Question	Level of Measurement	Analysis Plan	Inclusion		n
Pre-Operative Visit Form – Current Relevant Medical Conditions					N/A
Current Relevant Medical Conditions (Variable(s): CURCOND; CONDSPC)	Qualitative, nominal	Proportions, frequencies, column and row totals, missing proportion (if any). Listing of given specifications.	х	Х	

Table 6.2.3: Pre-Operative Visit Form - Current Relevant Medical Conditions

Evaluation Variable / Question	Level of Measurement	Analysis Plan	Inclusion		on
Pre-Operative Visit Form – Sul	ject Evaluation	L	IR	FR	N/A
Tobacco Use: (Variable(s): TOBCCO)	Qualitative, nominal	Proportions, frequencies, column and row totals, missing proportion (if any).	X	X	
Corticosteroids Taking: (Variable(s): CORTICO)	Qualitative, nominal	Proportions, frequencies, column and row totals, missing proportion (if any).	x	х	
Affected (Study) Tibia (Variable(s): AFFCTIB)	Qualitative, nominal	Proportions, frequencies, column and row totals, missing proportion (if any).	X	Х	
Fracture Classification: (Variable(s): FRUCLS)	Qualitative, nominal	Proportions, frequencies, column and row totals, missing proportion (if any).	X	Х	
Mechanism of Injury: (Variable(s): MECHINJ; OTHSPC)	Qualitative, nominal	Proportions, frequencies, column and row totals, missing proportion (if any). Listing of given specifications.	X	X	
Primary Indication: (Variable(s): PRIMIND)	Qualitative, nominal	Proportions, frequencies, column and row totals, missing proportion (if any). Listing of given specifications.	X	Х	
Previous History of Surgery to the Affected Tibia (Variable(s): PREVHIST)	Qualitative, nominal	Proportions, frequencies, column and row totals, missing proportion (if any). Listing of given specifications.		X	
Procedure 1 (Variable(s): PROCNM1)	Text, String				X

Procedure Date 1 (Variable(s): PROCDT1)	Quantitative, ratio Date/Time	Listing of comments and dates together identified by subject code/ID			Х
Procedure 2 (Variable(s): PROCNM2)	Text, String	Listing of comments and			Х
Procedure Date 2 (Variable(s): PROCDT2)	Quantitative, ratio Date/Time	dates together identified by subject code/ID			Х
Procedure 3 (Variable(s): PROCNM3)	Text, String	Listing of comments and			Х
Procedure Date 3 (Variable(s): PROCDT3)	Quantitative, ratio Date/Time	dates together identified by subject code/ID			Х
Procedure 4 (Variable(s): PROCNM4)	Text, String	Listing of comments and			Х
Procedure Date 4 (Variable(s): PROCDT4)	Quantitative, ratio Date/Time	dates together identified by subject code/ID			Х
Previous History of Surgery to the Contralateral Tibia (Variable(s): PREVHISTCONTR)	Qualitative, nominal	Proportions, frequencies, column and row totals, missing proportion (if any). Listing of given specifications.		х	
Procedure 1 (Variable(s): CONTRPROCNM1)	Text, String	Listing of comments and			Х
Procedure Date 1 (Variable(s): CONTRPROCDT1)	Quantitative, ratio Date/Time	dates together identified by subject code/ID			Х
Procedure 2 (Variable(s): CONTRPROCNM2)	Text, String	Listing of comments and			Х
Procedure Date 2 (Variable(s): CONTRPROCDT2)	Quantitative, ratio Date/Time	dates together identified by subject code/ID			Х
Procedure 3 (Variable(s): CONTRPROCNM3)	Text, String	Listing of comments and			Х
Procedure Date 3 (Variable(s): CONTRPROCDT3)	Quantitative, ratio Date/Time	dates together identified by subject code/ID			Х
Procedure 4 (Variable(s): CONTRPROCNM4)	Text, String	Listing of comments and			Х
Procedure Date 4 (Variable(s): CONTRPROCDT4)	Quantitative, ratio Date/Time	dates together identified by subject code/ID			Х
Creation of variable Number of previous history of surgery to the Affected Tibia by Subject (Variable(s): PROCNM1; PROCNM2; PROCNM3; PROCNM4)	Qualitative, nominal	Proportions, frequencies, column and row totals, missing proportion (if any).		X	
Creation of variable Number of previous history of surgery to the Contralateral Tibia by Subject (Variable(s): CONTRPROCNM1; CONTRPROCNM2; CONTRPROCNM3; CONTRPROCNM4)	Qualitative, nominal	Proportions, frequencies, column and row totals, missing proportion (if any).		x	
Weight Bearing (Variable(s): WEIGTBEAR)	Qualitative, nominal	Proportions, frequencies, column and row totals, missing proportion (if any).	X	X	
Weight Bearing Specification (Variable(s): WEIGTSPC)	Qualitative, nominal	Proportions, frequencies, column and row totals, missing proportion (if any).	X	X	
External Support Prior to the Tibia Fracture (Variable(s): EXTRSUPP)	Qualitative, nominal	Proportions, frequencies, column and row totals, missing proportion (if any).	X	Х	

Table 6.2.4: Pre-Operative Visit Form – Subject Evaluation Tables List

Evaluation Variable / Question	Level of Measurement	Analysis Plan	Inclusion		
Pre-Operative Visit Form – SF-36 Score (post fracture, prior to					N/A
surgery)			ш	ΓN	
In general, would you say your	Oualitative.	Proportions, frequencies,			
health is (Variable(c): GH01 PESPONSE)	nominal	column and row totals,			X
Compared to one year ago, how		missing proportion (if any).			
would you rate your health in	Qualitative,	Proportions, frequencies,			37
general now?	nominal	column and row totals,			X
(Variable(s): HT_RESPONSE)		missing proportion (if any).			
Vigorous activities, such as running,		Proportions, frequencies,			
lifting neavy objects, participating in strenuous sports	Qualitative,	column and row totals,			Х
(Variable(s): PF01 RESPONSE)	nommar	missing proportion (if any).			
Moderate activities, such as moving a		Proportions fraguencies			
table, pushing a vacuum cleaner,	Qualitative,	column and row totals			x
bowling, or playing golf	nominal	missing proportion (if any).			
(Variable(s): PF02_RESPONSE)		Proportions fraguencies			
Lifting or carrying groceries	Qualitative,	column and row totals.			x
(Variable(s): PF03_RESPONSE)	nominal	missing proportion (if any).			
Climbing soveral flights of stairs	Qualitative	Proportions, frequencies,			
(Variable(s): PF04 RESPONSE)	nominal	column and row totals,			Х
	nominar	missing proportion (if any).			
Climbing one flight of stairs	Qualitative,	Proportions, frequencies,			v
(Variable(s): PF05_RESPONSE)	nominal	missing proportion (if any)			л
		Proportions, frequencies.			
Bending, kneeling, or stooping	Qualitative,	column and row totals,			Х
(variable(s): PF06_RESPONSE)	nominal	missing proportion (if any).			
Walking more than a mile	Qualitative.	Proportions, frequencies,			
(Variable(s): PF07 RESPONSE)	nominal	column and row totals,			X
		Proportions frequencies			
Walking several hundred yards	Qualitative,	column and row totals.			x
(Variable(s): PF08_RESPONSE)	nominal	missing proportion (if any).			
Walking one hundred vards	Qualitative	Proportions, frequencies,			
(Variable(s): PF09 RESPONSE)	nominal	column and row totals,			Х
		missing proportion (if any).			
Bathing or dressing yourself	Qualitative,	column and row totals			x
(Variable(s): PF10_RESPONSE)	nominal	missing proportion (if any).			
Cut down the amount of time you	Qualitativa	Proportions, frequencies,			
spent on work or other activities	nominal	column and row totals,			Х
(Variable(s): RP01 RESPONSE)	nominui	missing proportion (if any).			
Accomplished less than you would	Qualitative,	Proportions, frequencies,			v
(Variable(s): RP02 RESPONSE)	nominal	missing proportion (if any).			Λ
Were limited in the kind of work or		Proportions, frequencies,			
other activities	Qualitative,	column and row totals,			Х
(Variable(s): RP03_RESPONSE)	nommai	missing proportion (if any).			
Had difficulty performing the work		Proportions from one			
other activities (for example it took	Qualitative,	column and row totals			x
extra effort)	nominal	missing proportion (if any).			
(Variable(s): RP04_RESPONSE)					
Cut down the amount of time you	Qualitative	Proportions, frequencies,			
spent on work or other activities	nominal	column and row totals,			X
(variable(s): KEUI_KESPONSE)		missing proportion (if any).			
like	Qualitative,	column and row totals			x
(Variable(s): RE02 RESPONSE)	nominal	missing proportion (if any).			
Did work or other activities less	Qualitativa	Proportions, frequencies,			
carefully than usual	nominal	column and row totals,			Х
(Variable(s): RE03 RESPONSE)		missing proportion (if any).			

	T	1			
During the past 4 weeks, to what extent has your physical health or emotional problems interfered with your normal social activities with family, friends, neighbors, or groups?	Qualitative, nominal	Proportions, frequencies, column and row totals, missing proportion (if any).			х
(Variable(s): SF01_RESPONSE) How much bodily pain have you had during the past 4 weeks? (Variable(s): BP01_RESPONSE)	Qualitative, nominal	Proportions, frequencies, column and row totals, missing proportion (if any).			X
During the past 4 weeks, how much did pain interfere with your normal work (including both work outside the home and housework)? (Variable(s): BP02_RESPONSE)	Qualitative, nominal	Proportions, frequencies, column and row totals, missing proportion (if any).			Х
Did you feel full of life? (Variable(s): VT01_RESPONSE)	Qualitative, nominal	Proportions, frequencies, column and row totals, missing proportion (if any).			Х
Have you been very nervous? (Variable(s): MH01_RESPONSE)	Qualitative, nominal	Proportions, frequencies, column and row totals, missing proportion (if any).			Х
Have you felt so down in the dumps that nothing could cheer you up? (Variable(s): MH02_RESPONSE)	Qualitative, nominal	Proportions, frequencies, column and row totals, missing proportion (if any).			Х
Have you felt calm and peaceful? (Variable(s): MH03_RESPONSE)	Qualitative, nominal	Proportions, frequencies, column and row totals, missing proportion (if any).			Х
Did you have a lot of energy? (Variable(s): VT02_RESPONSE)	Qualitative, nominal	Proportions, frequencies, column and row totals, missing proportion (if any).			Х
Have you felt downhearted and depressed? (Variable(s): MH04_RESPONSE)	Qualitative, nominal	Proportions, frequencies, column and row totals, missing proportion (if any).			Х
Did you feel worn out? (Variable(s): VT03_RESPONSE)	Qualitative, nominal	Proportions, frequencies, column and row totals, missing proportion (if any).			Х
Have you been happy? (Variable(s): MH05_RESPONSE)	Qualitative, nominal	Proportions, frequencies, column and row totals, missing proportion (if any).			Х
Did you feel tired? (Variable(s): VT04_RESPONSE)	Qualitative, nominal	Proportions, frequencies, column and row totals, missing proportion (if any).			Х
During the past 4 weeks, how much of the time has your physical health or emotional problems interfered with your social activities (like visiting friends, relatives, etc.)? (Variable(s): SF02_RESPONSE)	Qualitative, nominal	Proportions, frequencies, column and row totals, missing proportion (if any).			Х
I seem to get sick a little easier than other people (Variable(s): GH02 RESPONSE)	Qualitative, nominal	Proportions, frequencies, column and row totals, missing proportion (if any).			Х
I am as healthy as anybody I know (Variable(s): GH03_RESPONSE)	Qualitative, nominal	Proportions, frequencies, column and row totals, missing proportion (if any).			Х
I expect my health to get worse (Variable(s): GH04_RESPONSE)	Qualitative, nominal	Proportions, frequencies, column and row totals, missing proportion (if any).			Х
My health is excellent (Variable(s): GH05_RESPONSE)	Qualitative, nominal	Proportions, frequencies, column and row totals, missing proportion (if any).			Х
Physical Functioning (Variable(s): PFSCORE)	Quantitative, ratio	Case summary with number and percentage of valid cases/values, missing cases/values (if any) and total cases/values. Mean, median, interquartile range, maximum, minimum, standard deviation, 95%	Х	Х	

		confidence interval for mean,			
		Shapiro-Wilk Test.			
Role Physical (Variable(s): RPSCORE)	Quantitative, ratio	Case summary with number and percentage of valid cases/values, missing cases/values (if any) and total cases/values. Mean, median, interquartile range, maximum, minimum, standard deviation, 95% confidence interval for mean, Shapiro-Wilk Test.	х	х	
Bodily Pain (Variable(s): BPSCORE)	Quantitative, ratio	Case summary with number and percentage of valid cases/values, missing cases/values (if any) and total cases/values. Mean, median, interquartile range, maximum, minimum, standard deviation, 95% confidence interval for mean, Shapiro-Wilk Test.	х	x	
General Health (Variable(s): GHSCORE)	Quantitative, ratio	Case summary with number and percentage of valid cases/values, missing cases/values (if any) and total cases/values. Mean, median, interquartile range, maximum, minimum, standard deviation, 95% confidence interval for mean, Shapiro-Wilk Test.	х	х	
Vitality (Variable(s): VTSCORE)	Quantitative, ratio	Case summary with number and percentage of valid cases/values, missing cases/values (if any) and total cases/values. Mean, median, interquartile range, maximum, minimum, standard deviation, 95% confidence interval for mean, Shapiro-Wilk Test.	х	X	
Social Functioning (Variable(s): SFSCORE)	Quantitative, ratio	Case summary with number and percentage of valid cases/values, missing cases/values (if any) and total cases/values. Mean, median, interquartile range, maximum, minimum, standard deviation, 95% confidence interval for mean, Shapiro-Wilk Test.	x	x	
Role Emotional (Variable(s): RESCORE)	Quantitative, ratio	Case summary with number and percentage of valid cases/values, missing cases/values (if any) and total cases/values. Mean, median, interquartile range, maximum, minimum, standard deviation, 95% confidence interval for mean, Shapiro-Wilk Test.	X	X	
Mental Health (Variable(s): MHSCORE)	Quantitative, ratio	Case summary with number and percentage of valid cases/values, missing cases/values (if any) and total cases/values. Mean, median, interquartile range maximum minimum	X	X	

		standard deviation, 95% confidence interval for mean, Shapiro-Wilk Test.			
Total Physical Score (Variable(s): PCSSCORE)	Quantitative, ratio	Case summary with number and percentage of valid cases/values, missing cases/values (if any) and total cases/values. Mean, median, interquartile range, maximum, minimum, standard deviation, 95% confidence interval for mean, Shapiro-Wilk Test.	х	х	
Total Mental Score (Variable(s): MCSSCORE)	Quantitative, ratio	Case summary with number and percentage of valid cases/values, missing cases/values (if any) and total cases/values. Mean, median, interquartile range, maximum, minimum, standard deviation, 95% confidence interval for mean, Shapiro-Wilk Test.	х	X	

Table 6.2.5: Pre-Operative Visit Form – SF-36 Score (post fracture, prior to surgery) Tables List

